3.1.6 Evaluation of Site Effect

This is a multi-center study. Sites will not be pooled for any planned inferential analysis but may be pooled for subgroup analysis to assess the heterogeneity of treatment effects among pooled sites. The final pooling algorithm, if needed, will be specified before treatment unblinding and will be provided as an addendum to the SAP. Additionally, a review of by-site effects will be performed in the context of data listing review.

3.2 Analysis Populations

3.2.1 Intent-to-Treat (ITT) Population

The Intent-to-Treat (ITT) Population will include all participants randomized into the study. Treatment classification will be based on the randomized treatment.

3.2.2 Modified Intent-to-Treat (ITT) Population

The Modified ITT (mITT) Population will include all participants in the ITT Population who receive at least 1 dose of any study drug and have a Baseline value for the LDL-C assessment. Any

NewAmsterdam Pharma BV	CONFIDENTIAL	Statistical Analysis Plan
Protocol TA-8995-303		Version V2.0, 24 June 2021

efficacy measurement obtained after a participant receives a restricted lipid altering therapy¹, outside of the current study design, will be removed from the mITT analysis. Treatment classification will be based on the randomized treatment. The mITT Population will be used for the primary analysis of all efficacy endpoints.

3.2.3 Per-Protocol (PP) Population

The Per-Protocol (PP) Population will include all participants in the mITT Population who have a Baseline value for the LDL-C assessment, have a Day 57 value for the LDL-C assessment, and who did not experience a major protocol deviation that potentially impacted the primary efficacy endpoint. Major protocol deviations will be defined in the Protocol Deviation Plan within the trial master file to align with International Conference on Harmonization guidelines. The determination of membership in the PP Population will be made prior to study unblinding. The PP Population will be a secondary population for analysis of the primary efficacy endpoint.

3.2.4 Safety Population

The Safety Population will include all participants who receive at least 1 dose of any study drug. Treatment classification will be based on the actual treatment received. The Safety Population will be the primary population used for the safety analyses.

3.3 Subject Data and Study Conduct

3.3.1 Subject Disposition

Subject disposition will be presented for all randomized subjects. The count and percentage of subjects who are randomized, complete the study, complete the treatment, prematurely discontinue from the study, reasons for study discontinuation, and primary reason for early termination was due to COVID-19 will be summarized by treatment and in overall. For each scheduled visit, the count and percentage of subjects who could not completed in-person, partially completed, or performed virtually visit due to COVID-19 will be summarized by treatment. The denominator for calculating percentages will be based on the number of randomized subjects.

Data listing for subject disposition and exclusion and inclusion criteria violation will be provided.

3.3.2 Protocol Deviations

Protocol deviations will be identified based on the clinical data as defined in the Protocol Deviation Plan. The Protocol Deviation Plan will define all protocol deviations as either CSR reportable or non-CSR reportable deviations. Counts and percentages of subjects with CSR reportable protocol deviations by deviation category will be summarized by treatment and in total based on all randomized subjects. A listing of CSR-reportable protocol deviations will be generated.

3.3.3 Analysis Populations

Counts and percentages of subjects in each analysis population will be summarized by treatment and in total based on all randomized subjects. Reasons for exclusion from the PP population will also be summarized.

¹ Any lipid-altering therapy other than the investigational study drugs will be prohibited during the study.

3.3.4 Demographic and Baseline Characteristics

Subjects demographic and Baseline characteristics include, but are not limited to, the following:

- Age in years
- Sex
- Ethnicity
- Height (cm)
- Weight (kg)
- Stratification group: LDL-C value (<3.5 mmol/L [<135 mg/dL] or ≥3.5 mmol/L [≥135 mg/dL])
- Whether or not used statin therapy in the past

Demographic and Baseline characteristics will be summarized descriptively by treatment and in total for the mITT Population. If they differ from the mITT Population, summaries will also be provided for the ITT Population, the PP Population and the Safety Population.

3.3.5 Medical History

Medical history will be coded to system organ class and preferred term using the Medical Dictionary for Regulatory Activities (MedDRA) version 23.0. Counts and percentages of subjects with medical history by system organ class and preferred term will be summarized by treatment and in total based on all randomized subjects.

3.3.6 Concomitant Medications

Medication start and stop dates that are recorded on the Prior & Concomitant Medications case report form will be used to determine whether the medications are prior or concomitant to the study treatment. Concomitant medications are defined as those used on or after the first dose of study treatment. Prior medications are defined as those used prior to and stopped before the first dose of study treatment. All prior and concomitant medication verbatim terms will be coded using the World Health Organization (WHO) Drug Dictionary (WHO Drug Mar 2020G B). The numbers and percentages of subjects taking prior and concomitant medications in each treatment and in total will be summarized by anatomic and therapeutic chemical (ATC) class and preferred term for the Safety Population.

3.3.7 Study Drug Exposure and Compliance

Subjects' exposure to randomized study medication will be summarized with descriptive statistics for the Safety Population. Days of exposure is defined as:

date of last dose of study drug – date of first dose + 1

For those whose date of first dose from the initial blister card dispensed was not available, the date of randomization will be used to assign the date of first dose. For those who failed to provide the date of last dose of study drug, the earliest date between the end of treatment date and the date of end of study/early termination will be used.

A summary will be provided to display the count and percentage of subjects in each treatment with exposure in the following categories: <4 weeks, 4 - 8 weeks, 8 - 12 weeks and 12 weeks.

Summary statistics will be presented for percent overall compliance to study medication by treatment and in total. The count and percentage of subjects will also be tabulated by groups with overall compliance < 80%, 80% to 120%, and > 120%.

The percent overall compliance to obicetrapib tablets will be calculated as:

 $100 imes \frac{actual \ tablets \ taken}{expected \ study \ drug \ taken}$

The percent overall compliance to ezetimibe capsules will be calculated as:

$$100 imes \frac{\text{actual capsules taken}}{\text{expected study drug taken}}$$

The percent overall study drug compliance will be calculated as:

 $100 imes \frac{actual study drug taken}{expected study drug taken imes 2}$

Expected study drug taken = (the earliest date between the end of treatment date and the date of early termination) – the date of randomization + 1.

The number of actual study drug taken is the total number of study drug dispensed minus the total number of study drug returned, as reported on the CRF. If blister cards are not returned, it will be assumed that all tablets/capsules from that blister cards were used.

3.4 Efficacy Assessment

The mITT Population will be the primary population for the efficacy analyses. Efficacy will also be analyzed using the ITT Population and the PP Population as supportive analyses for select endpoints.

It is to highlight that LDL-C level will be collected using the following two approaches:

- 1. At each scheduled visit, LDL-C level will be calculated using the Friedewald formula;
- 2. In addition, at Baseline (Day 1) and at the end of the 8-week Treatment Period (Day 57), LDL-C will be measured for all patients by PUC¹.
- 3.4.1 Primary Efficacy Endpoint

Primary Analysis

The primary efficacy analysis is to evaluate the percent change from Day 1 to Day 57 in LDL-C (as determined by the Friedewald formula) for the combination therapy group compared to the placebo group. The percent change is calculated from Baseline to each measurement taken at Day 29, Day 57, and Day 85.

The percent change in LDL-C from Day 1 to Day 57 for each treatment is defined mathematically as μ_{jt} , where j stands for the jth treatment (*j*=0,1,2,3) and the subscript 0 refers to the placebo group; and *t* stands for time to visit at Day 29, Day 57, and Day 85 (*t*=1,2,3). The hypotheses testing to the percent change in LDL-C from Day 1 to Day 57 is then defined statistically as following:

 $H_0: \mu_{jt} - \mu_{0t} = 0, H_1: \mu_{jt} - \mu_{0t} \neq 0$, where *j*=1,2,3

NewAmsterdam Pharma BV	
Protocol TA-8995-303	

The primary efficacy analysis of the percent change from Day 1 to Day 57 in LDL-C will be performed using a mixed model for repeated measures (MMRM) approach. The analysis will include fixed effects for treatment, visit, and treatment-by-visit interaction, along with a covariate of the Baseline value as a continuous covariate. It is to note that randomization was stratified by categories of LDL-C value (<3.5 mmol/L [<135 mg/dL] or \ge 3.5 mmol/L [\ge 135 mg/dL]) only to ensure similar distribution of LDL-C across all treatment groups; however, the MMRM model will include the original scale of the LDL-C value as a continuous covariate. The Restricted Maximum Likelihood estimation approach will be used with an unstructured covariance matrix. The least squares means, standard errors, and 2-sided 95% confidence intervals for each treatment group, for the pairwise comparisons of the combination therapy, obicetrapib monotherapy, and ezetimibe monotherapy to placebo, and for the pairwise comparisons of combination therapy and obicetrapib monotherapy versus ezetimibe monotherapy will be provided. The treatment comparison will be performed using a 2-sided test at the $\alpha = 0.05$ level of significance.

The MMRM approach will include all available assessments of percent change in LDL-C from Baseline to Day 29, Day 57, and Day 85. The model assumes the data are missing at random (MAR). If any data are missing, the model will use all information from the other time points to estimate the mean treatment difference at the given time point. No imputation of missing data will be performed for the primary efficacy endpoint analysis.

The analysis will be implemented using SAS[®] Proc Mixed. The sample SAS code can be found below:

Note: USUBJID = unique subject identifier TREATMENT = 0 (Placebo), 1 (Ezetimibe monotherapy), 2 (Obicetrapib monotherapy), 3 (Combination therapy) VISIT = visit BASE = Baseline value PCHG = Percent change from Baseline proc mixed; class USUBJID TREATMENT VISIT; model PCHG = TREATMENT VISIT; model PCHG = TREATMENT BASE VISIT TREATMENT*VISIT / solution cl; Repeated VISIT / TYPE=UN sub=USUBJID; Ismeans VISIT*TREATMENT / cl diffs; run;

Sensitivity Analysis

Sensitivity analysis will be performed for the primary efficacy endpoint. In the first analysis, missing data will be imputed using a control-based pattern imputation model assuming the data are missing not at random (MNAR). The multiple imputation will be performed such that only observations from the placebo group are used to derive the imputation model for missing LDL-C values. Missing data at Day 29, 57, and 85 will be imputed using multiple imputation methodology in two steps. Initially, 25 data sets will be imputed for non-monotone missing values in the original dataset. In the second step the remaining monotone missing values will be imputed. Upon

completion of the trial, if the percentage of cases with incomplete data is larger than initially anticipated then the number of imputations will be increased for the final analysis.

The variables for the imputation model will consist of LDL-C values from Baseline and Days 29, 57, and 85. For each imputation dataset, the percent change from baseline to Day 57 will be analyzed using the MMRM model described above. The results from these 25 analyses will be combined to construct the treatment estimates using the parameter estimates and associated standard errors. Similarly, the difference of the adjusted treatment means (Combination therapy – Placebo) will be presented with the associated standard error and 95% confidence interval. Randomly chosen seed numbers will be selected for the analysis and will be retained.

In the second sensitivity analysis, the percent change from Day 1 to Day 57 in LDL-C, via the Friedewald formula, for the combination therapy group compared to the placebo group will be analyzed using an Analysis of Covariance (ANCOVA) model with fixed effects of treatment group and the Baseline LDL-C value as a continuous covariate. The least squares means, standard errors, and 2-sided 95% confidence intervals for each treatment group, for the pairwise comparisons of the combination therapy, obicetrapib monotherapy, and ezetimibe monotherapy to placebo will be provided. The treatment comparison will be performed using a 2-sided test at the $\alpha = 0.05$ level of significance. No imputation of missing data will be performed for this sensitivity analysis.

In the third sensitivity analysis, the percent change from Day 1 to Day 57 in LDL-C will be assessed where the LDL-C values will be measured by preparative ultracentrifugation (PUC), also referred to as beta quantification. The percent change from Day 1 to Day 57 in LDL-C by PUC for the combination therapy group compared to the placebo group will be analyzed using an ANCOVA similar to the model described in the second sensitivity analysis. No imputation of missing data will be performed for this sensitivity analysis.

In the fourth sensitivity analysis, a similar ANCOVA model as described above will be utilized for the assessment of percent change from Baseline to Day 57 in LDL-C as measured by PUC. In this analysis, missing data at Day 57 will be imputed using a last observation carried backward (LOCB) approach in which the next available LDL-C measurement, as measured by PUC, following Day 57 will be used in the analysis. The previous TULIP trial¹ observed similar values of percent change in LDL-C at Week 8 and 12, providing a rationale for the LOCB approach in this trial.

The ANCOVA model will be implemented using SAS[®] Proc GLM. The sample SAS code can be found below:

Note: USUBJID = unique subject identifier TREATMENT = 0 (Placebo), 1 (Ezetimibe monotherapy), 2 (Obicetrapib monotherapy), 3 (Combination therapy) BASE = Baseline value PCHG = Percent change from Baseline proc glm data=LDL_C; class TREATMENT; model PCHG = TREATMENT BASE / ss1 ss3; means TREATMENT;

NewAmsterdam Pharma BV Protocol TA-8995-303	CONFIDENTIAL	Statistical Analysis Plan Version V2.0, 24 June 2021
Ismeans TREATMENT / cov stder estimate " Ezetimibe monother estimate " Obicetrapib monoth estimate " Combination therap	apy: Placebo" TREATMENT - nerapy: Placebo" TREATMENT -	1010;
run;		

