# 5.3 Randomization and Blinding

Participants who meet all eligibility criteria will be randomized into the study. Participants will be randomized in a 1:1:1:1 ratio to the combination therapy, obicetrapib monotherapy, ezetimibe monotherapy, or placebo treatment groups. At randomization, participants will be stratified according to their Screening Visit (Visit 1) LDL-C value (<3.5 mmol/L [<135 mg/dL] or ≥3.5 mmol/L [≥135 mg/dL]). An automated interactive response technology (IRT) system will be used to assign the participant to 1 of the 4 treatment groups.

Participants, Investigators, the Clinical Research Organization, and the Sponsor will be blinded to all lipid results from Day 1 (Visit 2) for the first participant through the PK Visit (Visit 6) for the last participant in order to protect blinding to treatment assignment.

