2.2 Study Design

2.2.1 Overview

This study will be a placebo-controlled, double-blind, randomized Phase 2 study in participants with mild dyslipidemia to evaluate the efficacy, safety, and tolerability of obicetrapib and ezetimibe combination therapy. The study will take place at approximately 10 to 15 sites in North America and Europe as appropriate.

This study consists of a Screening Visit (Visit 1), a Treatment Period (8 weeks, Visits 2 to 4), a Safety Follow-up Visit (Visit 5), and a Pharmacokinetic Visit (Visit 6). The expected study duration for participants entering on the study since Screening Visit is approximately 20-weeks. Please refer to Table 1. Schedule of Procedures) below for details.

At the Screening Visit (Visit 1), participants will be required to sign an informed consent form (ICF) before any study-related procedures are performed. After signing the ICF, participants will be assessed for study eligibility. Participants will also receive counselling regarding the Therapeutic Lifestyle Changes diet and will receive instructions on how to follow this diet. Participants will be required to begin the diet starting at the Screening Visit.

Up to 2 weeks after the Screening Visit, participants will return to the site on Day 1 (Visit 2) to be randomized and begin treatment. Approximately 100 eligible participants (25 participants per treatment group) will be randomized in a 1:1:1:1 ratio to 1 of the following treatment groups:

- Combination therapy: 5 mg obicetrapib + 10 mg ezetimibe;
- Obicetrapib monotherapy: 5 mg obicetrapib + placebo ezetimibe;
- Ezetimibe monotherapy: placebo obicetrapib + 10 mg ezetimibe; or
- Placebo: placebo obicetrapib + placebo ezetimibe.

During the 8-week Treatment Period, the assigned study drugs will be administered by the participant orally and once daily on Days 1 through 57. Participants will return to the site every 4 weeks for efficacy, safety, pharmacokinetics (PK), and CETP mass assessments.

Participants will return to the site for a Safety Follow-up Visit (Visit 5) approximately 4 weeks after the end of the Treatment Period for safety, PK, and CETP mass assessments.

Participants will return to the site for a PK Visit (Visit 6) approximately 8 weeks after the end of the Treatment Period for PK and CETP mass assessments.

CONFIDENTIAL

Table 1. Schedule of Procedures

	0	Т	reatm		Safety	DIC	
N 12 - 14	Screening		Perio		Follow-up	PK	Early
Visit	1	2	3	4	5	6	Termination
Week	Up to -2	0	4	8	12	16	Visit

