2.2.4 Sample Size Determination

A sample size of at least 100 evaluable participants (ie, 25 participants per treatment group) will provide >90% power to detect a 30% difference in LDL-C reduction at Day 57 (SD 15%) for the combination therapy group compared to the placebo group at a 2-sided significance level of 0.05.

The sample size for this study was determined in order to provide sufficient power (>80%) for the analyses of the primary efficacy endpoint and secondary efficacy endpoints described in Section 2.3. The sample size calculations used values reported from a previous clinical trial involving obicetrapib (TA-8995) as a starting point for the assumptions of the treatment difference and standard deviation¹. This sample size will also contribute sufficient participant exposure and safety data.

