3.4.2 Secondary Efficacy Endpoints

Similar MMRM models will be developed to examine the percent change from Day 1 to Day 57 in LDL-C (by Friedewald formula) or ApoB. In order to maintain the overall Type I error rate, the secondary efficacy endpoints will be tested sequentially at the 0.05 significance level according to the pre-specified order of hierarchy.

- Percent change from Day 1 to Day 57 in LDL-C for the obicetrapib monotherapy group compared to the placebo group;
- Percent change from Day 1 to Day 57 in ApoB for the combination therapy group compared to the placebo group;
- Percent change from Day 1 to Day 57 in ApoB for the obicetrapib monotherapy group compared to the placebo group;
- Percent change from Day 1 to Day 57 in LDL-C for combination therapy group compared to the ezetimibe monotherapy group;
- Percent change from Day 1 to Day 57 in LDL-C for the obicetrapib monotherapy group compared to the ezetimibe monotherapy group;
- Percent change from Day 1 to Day 57 in LDL-C, for the ezetimibe monotherapy group compared to the placebo group; and
- Percent change from Day 1 to Day 57 in ApoB for the combination therapy group compared to the ezetimibe monotherapy group.

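### The efficacy models adjust for the Day 1 baseline but leave out the Screening LDL-C stratum used at randomisation; adding it would be a small, nearly free improvement

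*SAP*

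**What the plan says.** **Randomisation.** Protocol 5.3 states: "At randomization, participants will be stratified according to their Screening Visit (Visit 1) LDL-C value", with the cut at 3.5 mmol/L (135 mg/dL). SAP 2.2.2 says the same.

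**Baseline.** SAP 3.1.3 takes the last measurement before the first dose. Protocol Appendix A schedules a fasting lipid profile at both Visit 1 and Visit 2, and the Visit 2 sample is drawn before dosing. Baseline is therefore normally the Day 1 value, not the Screening value.

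**LDL-C models.** SAP 3.4.1 explains that stratification was "only to ensure similar distribution of LDL-C across all treatment groups; however, the MMRM model will include the original scale of the LDL-C value"; LDL-C thus enters uncategorised. The sample code fits treatment, BASE, visit and treatment-by-visit. The ANCOVA sensitivity models fit treatment and BASE. The logistic models in SAP 3.4.3 fit treatment and the Baseline variable, which Protocol 9.2.1.2 names as baseline LDL-C.

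**Other lipids.** SAP 3.4.2 states: "Similar MMRM models will be developed to examine the percent change from Day 1 to Day 57 in LDL-C (by Friedewald formula) or ApoB". BASE is described only as the Baseline value, and the SAP does not say which analyte's baseline it is in the ApoB models.

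**The concern.** The sentence in SAP 3.4.1 reads as though the covariate were the stratifying variable without its cut point. It is a different blood draw, taken up to two weeks later and after the participant has started the TLC diet (Protocol 3.1.1).

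For ApoB the gap is wider. Three of the seven hierarchical secondary comparisons are on ApoB. If BASE there is baseline ApoB, those models hold no LDL-C term at all.

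Forcing balance on a factor is a reason to model it. If the factor predicts outcome beyond the covariates already fitted, leaving it out means the standard error does not take credit for the balance achieved, and intervals are slightly wider than they need be. The Screening reading could add something even for LDL-C. The endpoint is percent change from a single Day 1 reading, so error in that reading passes into the outcome, and a second pre-treatment reading helps to separate error from true level.

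At stake are a few percent of variance and an analysis that matches the randomisation. No conclusion of the trial depends on it.

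**Working it through.** **1. Inputs from the documents.** 25 per group, four groups allocated 1:1:1:1, difference 30 points, SD 15, two-sided alpha 0.05 (SAP 2.2.4). Ezetimibe versus placebo 18.58% (Protocol 1.4). LDL-C reduction of 45.3% on 5 mg obicetrapib (Protocol 1.3).

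**2. The plan's power figure.** SE = 15 × √(2/25) = 4.243. Then 30/4.243 − 1.960 = 5.111, and Φ(5.111) = 0.9999998 (noncentral t with 48 df: 0.9999997). The stated >90% is met.

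**3. Can the stratum matter for power?** Suppose, generously, that it explained a further 10% of residual variance. SD becomes 15 × √0.90 = 14.23.
- 30-point difference: power is above 99.99% with or without the stratum.
- 18.58-point difference: power goes from Φ(18.58/4.243 − 1.960) = 99.2% to Φ(18.58/4.025 − 1.960) = 99.6%.

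**4. Precision for LDL-C, by simulation.** ANCOVA at Day 57, 100 participants, four arms, blocks of 4 within stratum, 2,000 trials per setting. All correlations and error sizes are assumptions, and a single-visit ANCOVA stands in for the MMRM.

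(a) *Percent change depends only on observed Day 1 LDL-C* (SD 15; Screening/Day 1 correlation 0.6-0.95; outcome correlation 0-0.5). The stratum cannot help by construction, and the SE rises by 0.1-0.4%. Example at Screening/Day 1 correlation 0.8 and outcome correlation 0.5:

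| Model | SE of a pairwise difference |
|---|---|
| No covariate | 4.24 |
| Stratum only | 3.97 |
| Continuous baseline (the plan) | 3.67 |
| Baseline plus stratum | 3.68 |

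(b) *Day 1 LDL-C is a noisy reading of a stable level*, with no treatment effect in any arm:

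| Reliability | SE, baseline | SE, baseline + stratum | SE cut | Variance cut, 1 − (ratio)² |
|---|---|---|---|---|
| 0.6 | 4.338 | 4.168 | 3.9% | 7.7% |
| 0.7 | 3.938 | 3.772 | 4.2% | 8.3% |
| 0.8 | 3.593 | 3.466 | 3.5% | 6.9% |
| 0.9 | 3.237 | 3.181 | 1.7% | 3.4% |

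Setting (b) is favourable. With W the Day 57 value and B the Day 1 value, percent change is 100(W/B − 1), so a small relative error in B moves it by about W/B times that error. With no effect W/B is near 1. With a 45.3% reduction it is 1 − 0.453 = 0.547, so Day 1 error counts for about half as much.

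(c) *Within-person CV 6-10%, total SD about 10-20, with and without a diet shift between Screening and Day 1*: variance of combination versus placebo falls by roughly 0.5-4.5%. This is the range carried forward.

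**5. What that means for an interval.** The unadjusted half-width at SD 15 is 1.96 × 4.243 = 8.3 points. A 0.5% variance cut narrows it by 8.3 × (1 − √0.995) = 0.02 points; a 4.5% cut by 8.3 × (1 − √0.955) = 0.19 points. Against 100 participants this is worth about 0.5 to 4.5 of them (100 × 0.005; 100 × 0.045).

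**6. ApoB with its own baseline.** Under the assumptions of (c), the variance cut is 0.3-3%. Over a wider grid (baseline ApoB/Screening LDL-C correlation 0.2-0.8, outcome coefficient for Screening LDL-C beyond baseline ApoB 0-0.3), the SE change runs from +0.3% to about −4%. The largest gain (3.971 to 3.821) needs the weakest correlation together with the strongest residual effect.

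**7. Type I error for LDL-C.** Simulated rates were 0.039-0.058 without the stratum and 0.043-0.061 with it. The Monte Carlo SE is √(0.05 × 0.95/2000) = 0.005. Neither model departs materially from 0.05.

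**The case against.** The strongest reply is that the SAP deals with the factor openly: the LDL-C models carry LDL-C on its continuous scale, which usually holds more than a two-level split. The table under 4(a) supports this. Continuous baseline gives 3.67 against 3.97 for the stratum alone, and adding the stratum to it gains nothing there. The protocol specifies the same covariate, so the two documents agree. This stands, and it rules out several stronger readings that a reader might infer:

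- *That every efficacy model ignores the stratification factor.* The LDL-C MMRM and ANCOVA models and the protocol's logistic models all adjust for baseline LDL-C. Only for ApoB and the other lipids might LDL-C be missing, and there the SAP is silent on BASE rather than explicit.
- *That standard errors are wrong or the tests invalid.* Step 7 shows no inflation, and in a randomised comparison leaving out a covariate does not bias the mean difference.
- *That the precision is free and certain.* Its sign depends on whether outcome tracks the observed Day 1 reading or an underlying stable level, and the documents give nothing to decide this. Diet starts at Screening, so part of the Screening/Day 1 difference may be real change.

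It can also be said that continuous Screening LDL-C would gain more (about 1.5-8% of variance under the assumptions of 4(c)). It would, but it is not the factor used in the randomisation. If the aim is an analysis that matches the design, the stratum is the simpler choice.

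The reply does not make the SAP's rationale complete. The Day 1 value is not the Screening value, and balance alone is no argument for leaving a factor out.

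**Conclusion.** The point holds as an improvement, not as an error. The Screening stratum is in no efficacy model. For LDL-C a close substitute is present; for ApoB and the other lipids there is none on the natural reading of BASE.

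The likely gain from adding it is about 0.5-4.5% of variance for LDL-C and 0.3-3% for ApoB, with a possible SE loss of about 0.1-0.4%. There is no bias, no Type I error inflation and no material effect on power. These sizes rest on an assumed within-person CV of 6-10% and assumed correlations; the documents report neither a Screening/Day 1 correlation nor a covariate R-squared. Low severity, moderate confidence.

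**What to change.** 1. Add the randomisation stratum (Screening LDL-C below, or at least, 3.5 mmol/L) as a fixed effect in the MMRM, ANCOVA and logistic models, alongside the continuous Baseline value of the analysed variable.
2. State in SAP 3.4.2 and 3.4.3 that BASE is the endpoint's own baseline, if that is intended.
3. Reword the sentence in SAP 3.4.1 so that continuous baseline LDL-C is no longer given as the reason for leaving the stratum out.

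The cost is SAP wording, one model term and one degree of freedom, using data already collected. In the logistic models the odds ratio becomes conditional on the stratum as well as on baseline, which the SAP should note.
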